Paternal polypharmacy would be a potential confounding variable included in the PS for NDD analysis. Maternal polypharmacy would be considered as a risk factor. For the child, polypharmacy after birth will not be considered as a risk factor in this study. This is because of the high potential of reverse causality; for example there is evidence that children with aberrant behaviours irrespective of diagnosis of NDD are more likely to receive psychotropic polypharmacy. Published literature also suggests subjects with ASD may also have comorbid psychiatric conditions requiring psychotropic treatment and in this regard it is not always possible to define temporality (27–29).

For the CM analysis the polypharmacy score will not be calculated because offspring whose parents were exposed to teratogens (risk factor when considered as maternal exposure and confounders when considered as paternal exposure), associated with maternal exposure in the literature, were already excluded from the CM cohort for the purpose of the comparative analyses (see section 9.3.3.2).

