### **9.3.3.2 Congenital malformations - additional considerations**

**Maternal exposure to teratogenic activity/foetal toxicity.** Offspring maternally exposed (three months prior to conception or during pregnancy) to drugs with known teratogenic (32) activity/foetal toxicity (see Annex 3. Additional Information) are at risk of developing the outcomes of interest for reasons other than valproate, i.e. due to intake of other drugs associated with the CM. These offspring will be excluded from the comparative, sensitivity and exploratory objective analyses.

**Paternal exposure to teratogenic activity.** Paternal exposure to prescription medications, has not been associated with birth defects (3). Nevertheless, offspring from fathers exposed (three months prior to conception) to drugs with known teratogenic (32) activity (based on literature regarding maternal exposure) (see Annex 3. Additional Information) will be excluded from the comparative, sensitivity and exploratory objective analyses.

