C02LA08	rauwolfia alkaloids, whole root and diuretics
C02LA09	syrosingopine and diuretics
C02LA50	combination of rauwolfia alkaloids and diuretics incl. other combinations
C02LA51	reserpine and diuretics, combinations with other drugs
C02LA52	rescinnamine and diuretics, combinations with other drugs
C02LA71	reserpine and diuretics, combinations with psycholeptics
C02LB01	methyldopa (levorotatory) and diuretics
C02LC01	clonidine and diuretics
C02LC05	moxonidine and diuretics
C02LC51	clonidine and diuretics, combinations with other drugs
C02LE01	prazosin and diuretics
C02LF01	guanethidine and diuretics

ATC code	Name (5 th level ATC, chemical substance)
C02LG01	dihydralazine and diuretics
C02LG02	hydralazine and diuretics
C02LG03	picodralazine and diuretics
C02LG51	dihydralazine and diuretics, combinations with other drugs
C02LG73	picodralazine and diuretics, combinations with psycholeptics
C02LK01	veratrum and diuretics
C02LL01	pargyline and diuretics
C02LX01	pinacidil and diuretics
C03AA01	bendroflumethiazide
C03AA02	hydroflumethiazide
C03AA03	hydrochlorothiazide
C03AA04	chlorothiazide
C03AA05	polythiazide
C03AA06	trichlormethiazide
C03AA07	cyclopenthiiazide
C03AA08	methyclothiazide
C03AA09	cyclothiazide
C03AA13	mebutizide
C03AB01	bendroflumethiazide and potassium
C03AB02	hydroflumethiazide and potassium
C03AB03	hydrochlorothiazide and potassium
C03AB04	chlorothiazide and potassium
C03AB05	polythiazide and potassium
C03AB06	trichlormethiazide and potassium
C03AB07	cyclopenthiiazide and potassium
C03AB08	methyclothiazide and potassium
C03AB09	cyclothiazide and potassium
C03AH01	chlorothiazide, combinations
C03AH02	hydroflumethiazide, combinations
C03AX01	hydrochlorothiazide, combinations
C03EA01	hydrochlorothiazide and potassium-sparing agents
C03EA02	trichlormethiazide and potassium-sparing agents

ATC code	Name (5 th level ATC, chemical substance)
C03EA03	epitizide and potassium-sparing agents
C03EA04	altizide and potassium-sparing agents
C03EA05	mebutizide and potassium-sparing agents
C03EA06	chlortalidone and potassium-sparing agents
C03EA07	cyclopentiazide and potassium-sparing agents
C03EA12	metolazone and potassium-sparing agents
C03EA13	bendroflumethiazide and potassium-sparing agents
C03EA14	butizide and potassium-sparing agents
C03EB01	furosemide and potassium-sparing agents
C03EB02	bumetanide and potassium-sparing agents
C03XA01	Tolvaptan
C07AA01	alprenolol
C07AA02	oxprenolol
C07AA03	pindolol
C07AA05	propranolol

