C07AA06	timolol
C07AA07	sotalol
C07AA12	nadolol
C07AA14	mepindolol
C07AA15	carteolol
C07AA16	tertatolol
C07AA17	bopindolol
C07AA19	bupranolol
C07AA23	penbutolol
C07AA27	cloranolol
C07AB01	practolol
C07AB02	metoprolol
C07AB03	atenolol
C07AB04	acebutolol
C07AB05	betaxolol
C07AB06	bevantolol
C07AB07	bisoprolol

ATC code	Name (5 th level ATC, chemical substance)
C07AB08	celiprolol
C07AB09	esmolol
C07AB10	epanolol
C07AB11	s-atenolol
C07AB12	nebivolol
C07AB13	talinolol
C07AB14	landiolol
C07AG01	labetalol
C07AG02	carvedilol
C08CA01	amlodipine
C08CA02	felodipine
C08CA03	isradipine
C08CA04	nicardipine
C08CA05	nifedipine
C08CA06	nimodipine
C08CA07	nisoldipine
C08CA08	nitrendipine
C08CA09	lacidipine
C08CA10	nilvadipine
C08CA11	manidipine
C08CA12	barnidipine
C08CA13	lercanidipine
C08CA14	cilnidipine
C08CA15	benidipine
C08CA16	clevidipine
C08CA51	amlodipine and celecoxib
C08CA55	nifedipine, combinations
C08CX01	mibefradil
C08DA01	verapamil
C08DA02	gallopamil
C08DA51	verapamil, combinations
C08DB01	diltiazem

ATC code	Name (5 th level ATC, chemical substance)
C08EA01	fendiline
C08EA02	bepridil
C08EX01	lidoflazine
C08EX02	perhexiline
C08GA01	nifedipine and diuretics
C08GA02	amlodipine and diuretics
C09AA01	captopril
C09AA02	enalapril
C09AA03	lisinopril
C09AA04	perindopril
C09AA05	ramipril
C09AA06	quinapril
C09AA07	benazepril
C09AA08	cilazapril
C09AA09	fosinopril
C09AA10	trandolapril
C09AA11	spirapril
C09AA12	delapril
C09AA13	moexipril
C09AA14	temocapril
C09AA15	zofenopril
C09AA16	imidapril
C09BA01	captopril and diuretics
C09BA02	enalapril and diuretics
C09BA03	lisinopril and diuretics
C09BA04	perindopril and diuretics
C09BA05	ramipril and diuretics
C09BA06	quinapril and diuretics
C09BA07	benazepril and diuretics
C09BA08	cilazapril and diuretics
C09BA09	fosinopril and diuretics
C09BA12	delapril and diuretics

ATC code	Name (5 th level ATC, chemical substance)
C09BA13	moexipril and diuretics
C09BA15	zofenopril and diuretics
C09BB02	enalapril and lercanidipine
C09BB03	lisinopril and amlodipine
C09BB04	perindopril and amlodipine
C09BB05	ramipril and felodipine
C09BB06	enalapril and nitrendipine
C09BB07	ramipril and amlodipine
C09BB10	trandolapril and verapamil
C09BB12	delapril and manidipine
C09BX01	perindopril, amlodipine and indapamide
C09BX02	perindopril and bisoprolol
C09BX03	ramipril, amlodipine and hydrochlorothiazide
C09BX04	perindopril, bisoprolol and amlodipine
C09CA04	Irbesartan
C09CA07	Telmisartan
C09CA09	Azilsartan

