C09DA04	Irbesartan
C09DA07	Hydrochlorothiazide, telmisartan
C09DB01	Valsartan, amlodipine
C09DB04	Amlodipine, telmisartan
C09DX01	Valsartan, hydrochlorothiazide, amlodipine besilate
C09DX04	Sacubitril, valsartan
C09DX07	Hydrochlorothiazide, irbesartan
C09XA02	Aliskiren
C09XA52	Hydrochlorothiazide, aliskiren
C10AA01	simvastatin
C10AA02	lovastatin
C10AA03	pravastatin
C10AA04	fluvastatin
C10AA05	atorvastatin
C10AA06	cerivastatin

ATC code	Name (5 th level ATC, chemical substance)
C10AA07	rosuvastatin
C10AA08	pitavastatin
C10AB01	clofibrate
C10AB02	bezafibrate
C10AB03	aluminium clofibrate
C10AB04	gemfibrozil
C10AB05	fenofibrate
C10AB06	simfibrate
C10AB07	ronifibrate
C10AB08	ciprofibrate
C10AB09	etofibrate
C10AB10	clofibride
C10AB11	choline fenofibrate
C10AC01	colestyramine
C10AC02	colestipol
C10AC03	colextran
C10AC04	Colesevelam
C10AD01	niceritrol
C10AD02	nicotinic acid
C10AD03	nicofuranose
C10AD04	aluminium nicotinate
C10AD05	nicotiny alcohol (pyridylcarbinol)
C10AD06	acipimox
C10AD52	nicotinic acid, combinations
C10AX01	dextrothyroxine
C10AX02	probucol
C10AX03	tiadenol
C10AX05	meglutol
C10AX06	omega-3-triglycerides incl. other esters and acids
C10AX07	magnesium pyridoxal 5-phosphate glutamate
C10AX08	policosanol
C10AX09	ezetimibe

ATC code	Name (5 th level ATC, chemical substance)
C10AX10	Alipogene tiparvovec
C10AX11	mipomersen
C10AX12	Lomitapide
C10AX13	evolocumab
C10AX14	alirocumab
C10AX15	bempedoic acid
C10BA01	lovastatin and nicotinic acid
C10BA02	simvastatin and ezetimibe
C10BA03	pravastatin and fenofibrate
C10BA04	simvastatin and fenofibrate
C10BA05	atorvastatin and ezetimibe
C10BA06	rosuvastatin and ezetimibe
C10BA07	rosuvastatin and omega-3 fatty acids
C10BA08	atorvastatin and omega-3 fatty acids
C10BA09	rosuvastatin and fenofibrate
C10BX01	simvastatin and acetylsalicylic acid
C10BX02	pravastatin and acetylsalicylic acid
C10BX03	atorvastatin and amlodipine
C10BX04	simvastatin, acetylsalicylic acid and ramipril
C10BX05	rosuvastatin and acetylsalicylic acid
C10BX06	atorvastatin, acetylsalicylic acid and ramipril
C10BX07	rosuvastatin, amlodipine and lisinopril
C10BX08	atorvastatin and acetylsalicylic acid
C10BX09	rosuvastatin and amlodipine
C10BX10	rosuvastatin and valsartan
C10BX11	atorvastatin, amlodipine and perindopril
C10BX12	atorvastatin, acetylsalicylic acid and perindopril
C10BX13	rosuvastatin, perindopril and indapamide
C10BX14	rosuvastatin, amlodipine and perindopril
C10BX15	atorvastatin and perindopril

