J01DD01	cefotaxime
J01DD02	ceftazidime
J01DD03	cefsulodin
J01DD04	ceftriaxone
J01DD05	cefmenoxime
J01DD06	latamoxef
J01DD07	ceftizoxime
J01DD08	cefixime
J01DD09	cefodizime
J01DD10	cefetamet
J01DD11	cefpiramide
J01DD12	cefoperazone
J01DD13	cefpodoxime
J01DD14	ceftibuten
J01DD15	cefdinir
J01DD16	cefditoren
J01DD17	cefcapene
J01DD18	cefteram
J01DD51	cefotaxime and beta-lactamase inhibitor
J01DD52	ceftazidime and beta-lactamase inhibitor
J01DD54	ceftriaxone, combinations
J01DD62	cefoperazone and beta-lactamase inhibitor
J01DD63	ceftriaxone and beta-lactamase inhibitor
J01DD64	cefpodoxime and beta-lactamase inhibitor

ATC code	Name (5 th level ATC, chemical substance)
J01DE01	cefepime
J01DE02	cefpirome
J01DE03	cefzopran
J01DF01	aztreonam
J01DF02	carumonam
J01DH02	meropenem
J01DH03	ertapenem
J01DH04	doripenem
J01DH05	biapenem
J01DH06	tebipenem pivoxil
J01DH51	imipenem and cilastatin
J01DH52	meropenem and vaborbactam
J01DH55	panipenem and betamipron
J01DI01	ceftobiprole medocaril
J01DI02	ceftaroline fosamil
J01DI03	faropenem
J01DI54	ceftolozane and beta-lactamase inhibitor
J01EA01	trimethoprim
J01EA02	brodimoprim
J01EA03	iclaprim
J01EB01	sulfaisodimidine
J01EB02	sulfamethizole
J01EB03	sulfadimidine
J01EB04	sulfapyridine
J01EB05	sulfafurazole
J01EB06	sulfanilamide
J01EB07	sulfathiazole
J01EB08	sulfathiourea
J01EB20	combinations
J01EC01	sulfamethoxazole
J01EC02	sulfadiazine
J01EC03	sulfamoxole

ATC code	Name (5 th level ATC, chemical substance)
J01EC20	combinations
J01ED01	sulfadimethoxine
J01ED02	sulfalene
J01ED03	sulfametomidine
J01ED04	sulfametoxydiazine
J01ED05	sulfamethoxy pyridazine
J01ED06	sulfaperin
J01ED07	sulfamerazine
J01ED08	sulfaphenazole
J01ED09	sulfamazone
J01ED20	combinations
J01EE01	sulfamethoxazole and trimethoprim
J01EE02	sulfadiazine and trimethoprim
J01EE03	sulfametrole and trimethoprim
J01EE04	sulfamoxole and trimethoprim
J01EE05	sulfadimidine and trimethoprim
J01EE06	sulfadiazine and tetroxoprim
J01EE07	sulfamerazine and trimethoprim
J01FA15	Telithromycin
J01GA01	streptomycin
J01GA02	streptoduocin
J01GB01	tobramycin
J01GB03	gentamicin
J01GB04	kanamycin
J01GB05	neomycin
J01GB06	amikacin
J01GB07	netilmicin
J01GB08	sisomicin
J01GB09	dibekacin
J01GB10	ribostamycin
J01GB11	isepamicin
J01GB12	arbakacin

ATC code	Name (5 th level ATC, chemical substance)
J01GB13	bekanamycin
J01GB14	plazomicin
J01MA01	ofloxacin
J01MA02	ciprofloxacin
J01MA03	pefloxacin
J01MA04	enoxacin
J01MA05	temafloxacin
J01MA06	norfloxacin

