ATC code	Name (5 th level ATC, chemical substance)	2 nd level ATC, therapeutic subgroup	1 st level ATC, anatomical main group
C02KX01	bosentan	Antihypertensives	Cardiovascular system
C02KX02	ambrisentan	Antihypertensives	Cardiovascular system
C02KX03	sitaxentan	Antihypertensives	Cardiovascular system
C02KX04	macitentan	Antihypertensives	Cardiovascular system
C02KX05	riociguat	Antihypertensives	Cardiovascular system
C03AA01	bendrofluazide = bendroflumethiazide	Diuretics	Cardiovascular system
C03AA03	hydrochlorothiazide	Diuretics	Cardiovascular system
C03AA04	chlorothiazide	Diuretics	Cardiovascular system
C03AA07	cyclopentiazide	Diuretics	Cardiovascular system
C03AA08	methyclothiazide	Diuretics	Cardiovascular system
C03AX01	valsartan and hydrochlorothiazide = hydrochlorothiazide, combinations	Diuretics	Cardiovascular system
C03BA02	quinethazone	Diuretics	Cardiovascular system
C03BA03	clopamide	Diuretics	Cardiovascular system
C03BA04	chlortalidone	Diuretics	Cardiovascular system
C03BA05	mefruside	Diuretics	Cardiovascular system
C03BA08	metolazone	Diuretics	Cardiovascular system
C03BA11	indapamide	Diuretics	Cardiovascular system

ATC code	Name (5th level ATC, chemical substance)	2nd level ATC, therapeutic subgroup	1st level ATC, anatomical main group
C03CA01	frusemide = furosemide	Diuretics	Cardiovascular system
C03CA02	bumetanide	Diuretics	Cardiovascular system
C03CC01	etacrynic acid	Diuretics	Cardiovascular system
C03DA01	spironolactone	Diuretics	Cardiovascular system
C03DA04	eplerenone	Diuretics	Cardiovascular system
C03DB01	amiloride	Diuretics	Cardiovascular system
C03DB02	triamterene	Diuretics	Cardiovascular system
C03XA01	tolvaptan	Diuretics	Cardiovascular system
C04AA01	isoxsuprine	Peripheral vasodilators	Cardiovascular system
C04AD03	oxpentifylline = pentoxifylline	Peripheral vasodilators	Cardiovascular system
C05AA05	betamethasone valerate = betamethasone acetate	Vasoprotectives	Cardiovascular system
C05AA06	fluorometholone	Vasoprotectives	Cardiovascular system
C05AA12	triamcinolone	Vasoprotectives	Cardiovascular system
C05AE03	diltiazem	Vasoprotectives	Cardiovascular system
C05BA03	heparin	Vasoprotectives	Cardiovascular system
C05BB02	lauromacrogol = polidocanol	Vasoprotectives	Cardiovascular system
C07AA01	alprenolol	Beta blocking agents	Cardiovascular system
C07AA02	oxprenolol	Beta blocking agents	Cardiovascular system

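### The teratogen code list behind the CM exclusion (Table 56) omits most combination-product codes of substances it lists singly, so some offspring that section 9.3.3.2 means to exclude stay in

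*Protocol*

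**What the plan says.** Section 9.3.3.2 sets the rule. For offspring of mothers exposed to a listed teratogenic or foetotoxic drug in the three months before conception or during pregnancy, it states: "These offspring will be excluded from the comparative, sensitivity and exploratory objective analyses". Offspring of fathers exposed in the three months before conception are removed from the same analyses, again by reference to Annex 3. The list in Annex 3 is Table 56.

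Section 9.3.3 (polypharmacy paragraphs after Table 4) relies on this exclusion: "For the CM analysis the polypharmacy score will not be calculated because offspring whose parents were exposed to teratogens" are taken to have been removed already.

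Table 56 identifies drugs by 5th-level ATC code, with one 4th-level exception (B03AC). Table 54, in the same annex, prints many combination codes, among them J01EE01 ("sulfamethoxazole and trimethoprim"), C09BA02 ("enalapril and diuretics") and C09DA07 ("Hydrochlorothiazide, telmisartan"). None of these three is in Table 56.

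Table 56 enters C03AX01, in the diuretic group, as "valsartan and hydrochlorothiazide = hydrochlorothiazide, combinations". Table 54 labels the same code only "hydrochlorothiazide, combinations".

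**The concern.** An exclusion that runs on ATC codes catches only what the list holds. A combination product has its own code, often in a different 4th-level group from its components. Even prefix matching on enalapril's code C09AA02 cannot reach C09BA02. If the combination code is missing, the same substance leads to exclusion when dispensed alone and to retention when dispensed in a combination.

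The result would be that some offspring exposed to substances the protocol itself lists as teratogens remain in the CM comparative, sensitivity and exploratory analyses. No CM polypharmacy score stands behind the exclusion to pick them up.

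**Working it through.** No sample size, power or error-rate figure is involved, and the plan gives no figure to reproduce. The check is a cross-comparison of two tables in Annex 3.

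**Inputs.** Combination codes printed in Table 54; single-substance and combination codes printed in Table 56.

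**Step 1: side by side.**
- *Trimethoprim and sulfonamides.* Table 56 has J01EA01, J01EC01 and J01EC02, then goes to J01FA09. Table 54 prints J01EE01 to J01EE07, each containing trimethoprim or sulfadiazine. None is in Table 56.
- *ACE inhibitors.* Table 56 has C09AA01 to C09AA10. It has nothing from C09BA, C09BB or C09BX. The Table 54 codes with a listed ACE inhibitor are C09BA01-09 (9), C09BB02-07 and C09BB10 (7), and C09BX01-04 (4).
- *Sartans and aliskiren.* Table 56 has seven sartans, hydrochlorothiazide and aliskiren singly. It omits C09DA04, C09DA07, C09DX07 and C09XA52 (4), all printed in Table 54. Table 54 labels C09DA04 with irbesartan only, but irbesartan is itself a listed substance.
- *Renin-angiotensin total omitted.* 9 + 7 + 4 + 4 = 24.

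**Step 2: is it a deliberate singles-only list?** No. Table 56 holds atorvastatin/ezetimibe (C10BA05) and rosuvastatin/ezetimibe (C10BA06) but not simvastatin/ezetimibe (C10BA02), although all four substances are listed singly. It holds twelve A10BD codes but not A10BD05, 06, 09 or 16, whose components are all listed. It holds C09DB01/02/04 and C09DX01/03/04 but no C09DA code.

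**Step 3: extent.** Denominator: Table 54 combination codes with at least one component listed singly in Table 56. Numerator: those whose own code is absent from Table 56. The codes were transcribed by hand, so the totals are approximate.

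| Table 54 codes | With a listed component | In Table 56 | Omitted |
|---|---|---|---|
| C09 combinations | 28 | 4 | 24 |
| C10B | 26 | 3 | 23 |
| C03 combinations | 14 | 1 | 13 |
| J01EE | 7 | 0 | 7 |
| A02BD | 13 | 0 | 13 |
| M01A combinations | 7 | 0 | 7 |
| A10BD | 12 | 8 | 4 |
| J05AR | 24 | 11 | 13 |
| G03AA/G03AB | 26 | 26 | 0 |
| All other groups | 78 | 23 | 55 |
| **Total** | **235** | **76** | **159** |

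Share omitted: 159 / 235 = 68%. Without the 26 contraceptive codes, which are fully covered: 159 / (235 − 26) = 159 / 209 = 76%. A few debatable codes would not overturn the majority.

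**Step 4: the valsartan row.** The only Table 56 row for valsartan with hydrochlorothiazide alone is C03AX01. Table 54 files hydrochlorothiazide with telmisartan at C09DA07 and with irbesartan at C09DX07. Table 56 itself files the triple product of amlodipine, hydrochlorothiazide and valsartan at C09DX01. The two-drug row is out of line with all three.

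**The case against.** The strongest reply is that the consequence is slight. CM is a secondary outcome. Table 56 is long and includes aspirin, ibuprofen, SSRIs, proton pump inhibitors, tetracyclines and contraceptives, so a parent on an omitted combination who was also dispensed any listed code in the window is still excluded. For fathers, section 9.3.3.2 itself says prescription exposure has not been associated with birth defects. Nothing in the protocol suggests that use of the omitted products differs between the valproate and comparator groups. All of this stands and limits the size of the point. It does not make the list do what the section says.

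A second reply is that the list rests on a cited source not available here, and the amendment log describes the Annex 3 lists as working lists that reflect the databases. Some omitted products may not have been dispensed in these countries. That is possible for individual codes, but the same log entry covers Table 54, which prints them, and it does not explain why one statin/ezetimibe product is in and another out.

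Three stronger readings are tempting and not supported:
- A reader might infer that the share of codes omitted is the share of exposed parents missed. Codes are not people, and the protocol gives no dispensing frequencies.
- A reader might infer that a valsartan/hydrochlorothiazide dispensing is certainly missed. The protocol prints no C09D code for that product, so misfiling is only inferred from neighbouring rows.
- A reader might infer that whole groups such as C03AB or A02BD belong on the list. C03AB02/05/06/09 and A02BD13/15 contain no substance on Table 56; adding them would exclude offspring for drugs the protocol does not class as teratogens.

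**Conclusion.** The point holds as a defect in the code list. Table 56 omits most of the Table 54 combination codes that contain a substance it lists singly (about 159 of 235), and no stated principle separates the included from the omitted. Applied as printed, section 9.3.3.2 keeps in the CM analyses any offspring whose parents' only listed exposure in the window is an omitted combination. This is contrary to its own wording, and the polypharmacy score that might have compensated has been dropped for CM.

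The number of offspring affected and the direction of any bias cannot be derived from the protocol. The effect on the CM odds ratio is probably small. The conclusion assumes that the exclusion is run on the printed codes and not by a separate search on substance. The CM sample-size figures and the NDD analyses are not affected, because the teratogen exclusion applies to CM only.

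**What to change.** Extend Table 56 code by code, not by whole ATC group, to every combination code with at least one component already on the table. From Table 54 this includes:
- J01EE01-07;
- C09BA01-09; C09BB02-07 and C09BB10; C09BX01-04; C09DA04/07; C09DX07; C09XA52;
- C10BA02 and the other omitted statin combinations in C10BA and C10BX;
- A10BD05/06/09/16;
- the qualifying codes in C03, A02BD and the remaining groups, leaving out C03AB02/05/06/09 and A02BD13/15.

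Check the valsartan/hydrochlorothiazide row (C03AX01) against the C09D filing used for other sartan/thiazide products, and add the matching code.

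Then re-run the CM exclusion step and the CM analyses that follow from it, and report how many further offspring leave each exposure group. That count would supply the size that the protocol cannot give.

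The cost is a code-list edit, one re-run and a slightly smaller CM cohort. No new substance is added to the list.

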**Table 57: AEDs excluding the study drugs**

ATC code	Name (5 th level ATC, chemical substance)	4 th level ATC, chemical subgroup
N03AA01	Methylphenobarbital	Barbiturates and derivatives
N03AA02	Phenobarbital	Barbiturates and derivatives

ATC code	Name (5th level ATC, chemical substance)	4th level ATC, chemical subgroup
N03AA03	Primidone	Barbiturates and derivatives
N03AA04	Barbexaclone	Barbiturates and derivatives
N03AA30	Metharbital	Barbiturates and derivatives
N03AB01	Ethotoin	Hydantoin derivatives
N03AB02	Phenytoin	Hydantoin derivatives
N03AB03	Amino(diphenylhydantoin) valeric acid	Hydantoin derivatives
N03AB04	Mephenytoin	Hydantoin derivatives
N03AB05	Fosphenytoin	Hydantoin derivatives
N03AB52	Phenytoin, combinations	Hydantoin derivatives
N03AB54	Mephenytoin, combinations	Hydantoin derivatives
N03AC01	Paramethadione	Oxazolidine derivatives
N03AC02	Trimethadione	Oxazolidine derivatives
N03AC03	Ethadione	Oxazolidine derivatives
N03AD01	Ethosuximide	Succinimide derivatives
N03AD02	Phensuximide	Succinimide derivatives
N03AD03	Mesuximide	Succinimide derivatives
N03AD51	Ethosuximide, combinations	Succinimide derivatives
N03AE01	Clonazepam	Benzodiazepine derivatives
N03AF01	Carbamazepine	Carboxamide derivatives
N03AF02	Oxcarbazepine	Carboxamide derivatives
N03AF03	Rufinamide	Carboxamide derivatives
N03AF04	Eslicarbazepine	Carboxamide derivatives
N03AG03	Aminobutyric acid	Fatty Acid derivatives
N03AG04	Vigabatrin	Fatty Acid derivatives
N03AG05	Progabide	Fatty Acid derivatives
N03AG06	Tiagabine	Fatty Acid derivatives
N03AX03	Sultiame	Other Antiepileptics
N03AX07	Phenacemide	Other Antiepileptics
N03AX10	Felbamate	Other Antiepileptics
N03AX11	Topiramate	Other Antiepileptics
N03AX12	Gabapentin	Other Antiepileptics
N03AX13	Pheneturide	Other Antiepileptics

ATC code	Name (5th level ATC, chemical substance)	4th level ATC, chemical subgroup
N03AX15	Zonisamide	Other Antiepileptics
N03AX16	Pregabalin	Other Antiepileptics
N03AX17	Stiripentol	Other Antiepileptics
N03AX18	Lacosamide	Other Antiepileptics
N03AX19	Carisbamate	Other Antiepileptics
N03AX21	Retigabine	Other Antiepileptics
N03AX22	Perampanel	Other Antiepileptics
N03AX23	Brivaracetam	Other Antiepileptics
N03AX24	Cannabidiol	Other Antiepileptics
N03AX30	Beclamide	Other Antiepileptics

ATC: Anatomical Therapeutic Chemical

Table 58: AEDs all

ATC code	Name (5th level ATC, chemical substance)	4th level ATC, chemical subgroup
N03AA01	methylphenobarbital	Barbiturates and derivatives
N03AA02	phenobarbital	Barbiturates and derivatives
N03AA03	primidone	Barbiturates and derivatives
N03AA04	barbexaclone	Barbiturates and derivatives
N03AA30	metharbital	Barbiturates and derivatives
N03AB01	ethotoin	Hydantoin derivatives
N03AB02	phenytoin	Hydantoin derivatives
N03AB03	amino(diphenylhydantoin) valeric acid	Hydantoin derivatives
N03AB04	mephenytoin	Hydantoin derivatives
N03AB05	fosphenytoin	Hydantoin derivatives
N03AB52	phenytoin, combinations	Hydantoin derivatives
N03AB54	mephenytoin, combinations	Hydantoin derivatives
N03AC01	paramethadione	Oxazolidine derivatives
N03AC02	trimethadione	Oxazolidine derivatives
N03AC03	ethadione	Oxazolidine derivatives
N03AD01	ethosuximide	Succinimide derivatives
N03AD02	phensuximide	Succinimide derivatives
N03AD03	mesuximide	Succinimide derivatives
N03AD51	ethosuximide, combinations	Succinimide derivatives
N03AE01	clonazepam	Benzodiazepine derivatives
N03AF01	carbamazepine	Carboxamide derivatives
N03AF02	oxcarbazepine	Carboxamide derivatives
N03AF03	rufinamide	Carboxamide derivatives
N03AF04	eslicarbazepine	Carboxamide derivatives
N03AG01	valproic acid *	Fatty Acid derivatives
N03AG02	valpromide *	Fatty Acid derivatives
N03AG03	aminobutyric acid	Fatty Acid derivatives
N03AG04	vigabatrin	Fatty Acid derivatives
N03AG05	progabide	Fatty Acid derivatives
N03AG06	tiagabine	Fatty Acid derivatives
N03AX03	sultiame	Other Antiepileptics
N03AX07	phenacemide	Other Antiepileptics
N03AX09	lamotrigine *	Other Antiepileptics

ATC code	Name (5th level ATC, chemical substance)	4th level ATC, chemical subgroup
N03AX10	felbamate	Other Antiepileptics
N03AX11	topiramate	Other Antiepileptics
N03AX12	gabapentin	Other Antiepileptics
N03AX13	pheneturide	Other Antiepileptics
N03AX14	levetiracetam *	Other Antiepileptics
N03AX15	zonisamide	Other Antiepileptics
N03AX16	pregabalin	Other Antiepileptics
N03AX17	stiripentol	Other Antiepileptics
N03AX18	lacosamide	Other Antiepileptics
N03AX19	carisbamate	Other Antiepileptics
N03AX21	retigabine	Other Antiepileptics
N03AX22	perampanel	Other Antiepileptics
N03AX23	brivaracetam	Other Antiepileptics
N03AX24	cannabidiol	Other Antiepileptics
N03AX30	beclamide	Other Antiepileptics

AED: Anti-Epileptic Drug, ATC: Anatomical Therapeutic Chemical

\* Study drugs

